To ensure that the desired factor IX activity plasma level has been attained, careful monitoring using an appropriate factor IX activity assay is advised and, if necessary, appropriate adjustments to the dose and the frequency of repeated infusions should be performed. When using an *in vitro* thromboplastin time (aPTT)-based one stage clotting assay for determining factor IX activity in patients' blood samples, plasma factor IX activity results can be significantly affected by both the type of aPTT reagent and the reference standard used in the assay. This is of particular importance when changing the laboratory and/or reagents used in the assay.

The number of units of factor IX administered is expressed in International Units (IU), which are related to the current World Health Organization (WHO) standard for factor IX products. Factor IX activity in plasma is expressed either as a percentage (relative to normal human plasma) or in International Units (relative to an International Standard for factor IX in plasma).

One International Unit (IU) of factor IX activity is equivalent to that quantity of factor IX in one milliliter of normal human plasma.

On-demand treatment

The calculation of the required dose of factor IX is based on the empirical finding that 1 International Unit (IU) factor IX per kg body weight raises the plasma factor IX activity by 0.9 IU/dL (range from 0.5 to 1.4 IU/dL) or 0.9% of normal activity in patients aged 12 years and older (for further details, .

The required dose is determined using the following formula:

Patients aged 12 years and older

$$\text{Required units} = \text{body weight (kg)} \times \frac{\text{desired factor IX rise}}{(\% \text{ or (IU/dL)}} \times \frac{\text{reciprocal of observed recovery}}{(\text{dL/kg})}$$

For an incremental recovery of 0.9 IU/dL per IU/kg, the dose is calculated as follows:

$$\text{Required units} = \text{body weight (kg)} \times \frac{\text{desired factor IX rise}}{(\% \text{ or (IU/dL)}} \times 1.1 \text{ dL/kg}$$

The amount to be administered and the frequency of administration should always be oriented to the clinical effectiveness in each individual case.

In the case of the following hemorrhagic events, the factor IX activity should not fall below the given plasma activity level (in % of normal or IU/dL) in the corresponding period. The following table can be used to guide dosing in bleeding episodes and surgery:

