Degree of hemorrhage/Type of surgical procedure	Factor IX level required (%) or (IU/dL)	Frequency of doses (hours)/Duration of therapy (days)
Hemorrhage Early hemarthrosis, muscle bleeding or oral bleeding More extensive hemarthrosis, muscle bleeding or hematoma Life-threatening hemorrhages.	20 – 40 30 – 60 60 – 100	Repeat every 24 hours. At least 1 day, until the bleeding episode, as indicated by pain, resolves or healing is achieved. Repeat infusion every 24 hours for 3–4 days or more, until pain and acute disability are resolved. Repeat infusion every 8 to 24 hours until threat is resolved.
Minor Surgery Minor surgery including tooth extraction	30 – 60	Every 24 hours, at least 1 day, until healing is achieved.
Major surgery	80 – 100 (pre- and postoperative)	Repeat infusion every 8 to 24 hours until adequate wound healing occurs, then provide therapy for at least another 7 days to maintain a factor IX activity of 30% to 60% (IU/dl).

Careful monitoring of replacement therapy is especially important in cases of major surgery or life-threatening hemorrhages.

Prophylaxis

For long-term prophylaxis against bleeding in patients with severe hemophilia B, the usual doses are 40 to 60 IU of factor IX per kilogram of body weight at intervals of 3 to 4 days for patients aged 12 years and older. In some cases, depending upon the individual patient’s pharmacokinetics (PK), age, bleeding phenotype and physical activity, shorter dosage intervals or higher doses may be necessary.

Continuous infusion

Do not administer RIXUBIS by continuous infusion.

Pediatric population

On-demand treatment:

The calculation of the required dose of factor IX is based on the empirical finding that 1 IU factor IX per kg body weight raises the plasma factor IX activity by 0.7 IU/dL (range from 0.31 to 1.0 IU/dL) or 0.7% of normal activity in patients under 12 years of age .

The required dosage is determined using the following formula:

Patients under 12 years of age:

$$\text{Required units} = \text{body weight (kg)} \times \frac{\text{desired factor IX rise}}{(\% \text{ or (IU/dL)})} \times \frac{\text{reciprocal of}}{\text{observed recovery (dL/kg)}}$$

For an incremental recovery of 0.7 IU/dL per IU/kg, the dose is calculated as follows:

$$\text{Required units} = \text{body weight (kg)} \times \frac{\text{desired factor IX rise}}{(\% \text{ or (IU/dL)})} \times 1.4 \text{ dL/kg}$$

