9.3.2 Variables for assessing the secondary endpoints

9.3.2.1 Effectiveness of on-demand treatment

(see [APPENDIX 1](#))

- Overall effectiveness assessment for on-demand treatment with an “excellent-to-poor” 4-point scale, as rated by the patients or care-giver, also a rating of the severity of bleeding (mild, moderate, severe) (for details, see Appendix 1, [Table 3](#))
- Total weight-adjusted dose required for bleeding episode resolution
- Number of rFIX (RIXUBIS) infusions required for bleeding episode resolution.
- For perioperative treatment:
 - Type and severity of the surgical intervention
 - Intraoperative and postoperative effectiveness according to an “excellent-to-poor” 4-point scale (surgery) assessed by the physicians
 - Total weight-adjusted dose and number of infusions of rFIX (RXUBIS) required to cover the surgical procedure
 - Number of days spent in hospital related to the surgery
 - Need for supplemental hemostatic therapy (i.e. tranexamic acid, etc.).

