9.7.3.3 Methods of Analysis for Effectiveness Criteria

The annualized rate of bleeding episodes in joints, target joints, and other anatomical locations for the two independent samples (on-demand or prophylaxis) will be summarized. The frequency distribution for the number of infusions for bleed treatment will be reported for each of the on-demand and prophylaxis treatment regimens. The median number of infusions per bleeding episode for each subject will be calculated and the median for subjects in each treatment regimen will be compared using the Mann-Whitney (Wilcoxon-Rank Sum) test. The total weight-adjusted dose (IU/kg) per bleeding episode per subject will be described for both the on-demand and prophylaxis treatment regimens and will be compared using the Mann-Whitney (Wilcoxon-Rank Sum) test.

Corresponding to all treated FIX (RIXUBIS) bleeding episodes, the following parameters will be computed separately by treatment regimen (prophylaxis, on-demand):

Total number of subjects infused
Total bleed exposure days
Total number of bleed treatment infusions
Units administered per subject, per infusion (IU)
Units administered per subject, per bleed (IU)
Annualized units administered for bleed treatment, per subject (IU)
Total units administered for bleed treatment, per subject (IU)
Weight-adjusted dose per subject, per bleed (IU/kg)
Weight-adjusted dose per subject, per infusion (IU/kg)
Annualized weight-adjusted dose for bleed treatment, per subject (IU/kg)
Total weight-adjusted dose for bleed treatment, per subject (IU/kg)

Assessment of effectiveness:

Corresponding to subjects given prophylactic infusions (RIXUBIS) in this study, the following parameters will be computed by treatment regimen (prophylaxis, on-demand):

Total number of subjects infused
Total exposure days
Total number of infusions
Number of unique lots used
Units administered per subject, per infusion (IU)
Units administered per subject, per week (IU)
Units administered per subject, per month (IU)
Annualized units administered, per subject (IU)
Total units administered, per subject (IU)
Weight-adjusted dose per subject, per infusion (IU/kg)
Weight-adjusted dose per subject, per week (IU/kg)
Weight-adjusted dose per subject, per month (IU/kg)
Annualized weight-adjusted dose, per subject (IU/kg)
Total weight-adjusted dose, per subject (IU/kg)

The occurrence of new target joints and bleeding episodes used to assess new target joints will be summarized by treatment regimen.

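### The IU/kg-per-bleed comparison between on-demand and prophylaxis is not stratified by age, although the protocol's own dose formulas give under-12s about 1.27 times the IU/kg

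*Protocol*

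**What the plan says.** Section 9.7.3.3 fixes both the grouping and the test. Total IU/kg "per bleeding episode per subject will be described for both the on-demand and prophylaxis treatment regimens and will be compared using the Mann-Whitney" (Wilcoxon rank sum) test. Neither that section nor any other names a stratum or covariate for it. The variable itself is listed under on-demand effectiveness in Section 9.3.2.1.

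Section 7.1 gives two dose formulas, split at age 12. From 12 years, 1 IU/kg "raises the plasma factor IX activity by 0.9 IU/dL (range from 0.5 to 1.4 IU/dL"), and "For an incremental recovery of 0.9 IU/dL per IU/kg, the dose is calculated as follows": weight times desired rise times 1.1 dL/kg. Under 12 years, 1 IU/kg "raises the plasma factor IX activity by 0.7 IU/dL (range from 0.31 to 1.0 IU/dL"), and "For an incremental recovery of 0.7 IU/dL per IU/kg, the dose is calculated as follows": weight times desired rise times 1.4 dL/kg. The same section applies the adult table of target levels and infusion frequency to children.

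Under Section 9.1 the treating physician decides the regimen. The inclusion criteria in Section 9.2.3.1 set no age limit. Sections 9.1 and 9.5 both say that no hypothesis testing will be applied. Section 9.9 acknowledges large differences in treatment approach and dosing, but no adjustment of this comparison follows from it.

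**The concern.** Age at the 12-year cut is linked to the outcome by the protocol's own arithmetic, and it precedes the choice of regimen. In routine care nothing makes the share of children equal in the two regimen groups. An unstratified rank test then mixes two things: whether a regimen goes with more product per bleed, and how many children are in each group.

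A significant result would naturally be read as one regimen needing more factor per bleed. A null result would be read as no difference. Either could come from the age mix alone. The issue does not depend on several bleeds per subject being correlated: it remains with exactly one value per subject.

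**Working it through.** **Inputs from the protocol.** Recovery is 0.9 (12 and over) and 0.7 (under 12) IU/dL per IU/kg, with multipliers 1.1 and 1.4 dL/kg (Section 7.1). There are about 80 subjects (Section 9.5). No significance level is stated.

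**Assumed, because the documents do not give them.** Under-12 share by regimen; splits of 40+40 and 60+20 (prophylaxis first); log-normal scatter between subjects; two-sided 5% level; every subject contributes one value.

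**Step 1: the plan's own multipliers.** 1/0.9 = 1.11 (stated 1.1) and 1/0.7 = 1.43 (stated 1.4). Both reproduce.

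**Step 2: the age ratio.** 1.4/1.1 = 1.27 (unrounded, 0.9/0.7 = 1.29). For a rise of 30 IU/dL: 30 × 1.1 = 33 IU/kg and 30 × 1.4 = 42 IU/kg.

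**Step 3: the shift between regimens from age mix alone.** The ratio of geometric means is (1.4/1.1) raised to the difference in under-12 share. For 40% versus 10% this is 1.273^0.30 = 1.075, so the group with more children looks about 7.5% higher. A true within-age difference of the same size in the other direction (1/1.075 = 0.93) would be cancelled.

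**Step 4: what the test does.** Simulated Mann-Whitney test with no regimen effect within age (6,000 runs per setting; simulation error about half a point at most settings):

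| Under 12, prophylaxis vs on-demand | Log-SD | Rejects, 40+40 | Rejects, 60+20 |
|---|---|---|---|
| 25% vs 25% | 0.25 to 0.6 | about 5% | about 5% |
| 25% vs 10% | 0.25 to 0.35 | 6–9% | 6–9% |
| 25% vs 10% | 0.5 to 0.6 | 5–6% | 5–6% |
| 40% vs 10% | 0.25 | 21–22% | 17% |
| 40% vs 10% | 0.35 | 13% | 11% |
| 40% vs 10% | 0.5 | 9% | 8% |
| 40% vs 10% | 0.6 | 7% | 7% |

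A second version added extra scatter: 30% of subjects in both groups had a dose factor of 1.5, for more extensive bleeds. For 40% versus 10% under 12 and coefficients of variation of 0.25, 0.4 and 0.6, rejection was 15.6%, 10.5% and 7.6% (40+40) and 12.4%, 9.1% and 7.6% (60+20). These fall in the same range.

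**Step 5: after stratifying.** A van Elteren-type test stratified by age rejects in about 5% (4.2% to 5.6%) in every setting of the table.

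**Step 6: how thin the stratum gets.** At 10% under 12, the on-demand group has 40 × 0.10 = 4 or 20 × 0.10 = 2 such subjects.

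**The case against.** **Left to the SAP.** Strata and subgroup tables are often left to the SAP, which Section 14.1 lists as a separate document and which is not at hand. That would answer a protocol that was silent. This one names the test and the two groups being compared, and a reader would take that as an unstratified test. A SAP could still add strata, but the stated method should not depend on it.

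**Descriptive study.** The related objective is to describe, no decision hangs on the p-value, and if the groups differ in age their dose distributions really do differ. This has force: the table of doses is not wrong. What does not survive is attaching a test whose result cannot separate regimen from age. Dropping the test is accordingly one of the two remedies.

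**Assumed magnitude.** This stands. No age mix by regimen is given; the only age figures are 23 of 99 under 12 in the development programme (Section 7.1). Total dose per bleed may also scatter widely, since recovery and infusion counts vary, and that pulls rejection towards 5%. Subjects without a bleed contribute nothing (24 of 56 on prophylaxis had none in the pivotal study, Section 7.2), so the effective numbers may be smaller. Dosing is individualised too, so 1.27 is a guide rather than a fixed ratio.

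**Bleed severity.** A reader might infer that severity should be a second stratum, since the required levels rise ("20 – 40 30 – 60 60 – 100") and a more extensive bleed calls for "Repeat infusion every 24 hours for 3–4 days or more, until pain and acute disability are resolved". The documents do not support that step. The recorded rating ("also a rating of the severity of bleeding (mild, moderate, severe") is not mapped to the posology categories. Severity may itself be affected by prophylaxis, so stratifying on it could remove part of what is being compared. One value per subject and severity level would also put the same subject in several strata.

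**Infusions per bleed.** A reader might want the same age split for this comparison. Section 7.1 applies the adult frequency table to children, and the shares resolved with 1 or 2 infusions are similar (84.7% and 88.5%, Section 7.2), so that is unsupported.

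**Conclusion.** The point holds for age. Section 9.7.3.3 fixes an unstratified test of IU/kg per bleed between groups formed by physician choice, while the protocol's own formulas separate subjects under 12 from older ones by a factor of about 1.27. If the under-12 share differs between regimens, the result is biased, in a direction set by which regimen has more children. For 40% versus 10%, the bias is about 7.5% in geometric mean, and rejection is about 7% to 21% instead of 5%. Those figures rest on the assumed mix, scatter, split and 5% level.

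Two stronger readings should be avoided. Pooling ages does not by itself inflate the error: with equal mixes the test stays at about 5%, and at 25% versus 10% with wide scatter it barely moves. Rejection in more than half of trials can be produced, but only with an extreme mix (60% versus 0% under 12) and low scatter (log-SD 0.25), which nothing in the documents suggests. The comparison is secondary and the remedy is cheap, so this should be corrected but does not threaten the primary description. No dose is judged here.

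**What to change.** In Section 9.7.3.3, state that the IU/kg summaries by regimen are shown separately for subjects under 12 and for those 12 and over. Then choose one of two courses for the between-regimen comparison:

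- Keep it descriptive and remove the test, which agrees with Sections 9.1 and 9.5.
- Keep a test, but make it a van Elteren test stratified by age (under 12, 12 and over) on one value per subject, such as the subject's median IU/kg per bleed.

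Tabulate dose by recorded bleed severity descriptively, without using severity as a stratum.

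The cost is a sentence or two and extra table columns. Year of birth is already collected (Section 9.2.6), as is bleed severity (Sections 9.2.6 and 9.3.2.1). Because follow-up lasts four years and only the year of birth is recorded, the text should also say at which time age is taken, for example at enrolment, for subjects who pass 12 during the study. The main drawback is that the under-12 on-demand stratum may be small or empty. The stratified test would then rest almost wholly on subjects aged 12 and over, and the report should say so.

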9.7.3.4 Secondary Endpoints

(See Section [9.3.2](#))

9.7.3.4.1 Assessment of hemostatic effectiveness on-demand treatment

Total number (%) of treated bleeds and their corresponding hemostatic effectiveness ratings using an “excellent-to-poor” 4-point Likert scale as assessed by the subjects/ caregiver for treatments given at home, or by the investigator for treatments given in the hospital/clinic.

Separate ABRs will be provided for on-demand treatment, providing the minimum observed period is fulfilled (>90 days).

9.7.3.4.2 Methods of Analysis for Safety Endpoints

The analysis of AEs will be descriptive. All AEs will be categorized according to the MedDRA dictionary and summarized by system organ class and preferred term. AEs for which the investigator does not state the relationship to RIXUBIS administration will be included. All AEs will be cross-tabulated for relatedness, seriousness, and severity.

9.7.3.4.3 Joint Health/Function Outcomes

The methods of analysis for the secondary effectiveness endpoints ([APPENDIX 2](#)) are, if available:

- Physical exam using only the pain, bleeding, and physical exam parameters of the Hemophilia Joint Health Score (HJHS) score will be summarized for timepoints 0 (baseline), 12, 24, 36 and 48 months (termination visit) after study start (if available). Linear interpolation (for any time interval) and line extrapolation (for up to 0.5 years) will be used to derive an estimate of the score at these timepoints.
- MRI scoring will be summarized for timepoints 0, 12, 24, 36 and 48 months (termination visit) after study start (if available). Linear interpolation (for any time interval) and line extrapolation (for up to 0.5 years) will be used to derive an estimate of the score at these timepoints.
- Radiographs using the Pettersson score will be summarized for timepoints 0, 12, 24, 36 and 48 months (termination visit) after study start (if available). Linear interpolation (for any time interval) and line extrapolation (for up to 0.5 years) will be used to derive an estimate of the score at these timepoints.
- Number of invasive surgical procedures, such as (not exclusively orthopedic) surgery, radiosynovectomy, and chemosynovectomy per year per subject.

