 - FIX regimen used at the time of inhibitor detection
 - Maximum historical titer
 - Local laboratory cut off value for positive inhibitor titer
 - History of ITI therapy, if any, including FIX product and regimen used.
 - Date(s) of inhibitor disappearance
 - Most recent FIX inhibitor test results.
- Current RIXUBIS treatment
 - Dosage and dosing intervals
 - Regimen start date

- Total EDs to RIXUBIS at screening visit
Where exact numbers of EDs is not available, one of the following ranges should be selected: 0, 1-4, 5-20, 21-50, 51-100, 101-150 or >150.
- FIX product used prior to RIXUBIS treatment initiation (maximal retrospective time-period of 12 months before treatment initiation)
 - Name of product, dosage and dosing interval
 - Regimen start and end date
 - Total EDs to FIX products at screening visit
Where exact numbers of EDs is not available, one of the following ranges should be selected: 0, 1-4, 5-20, 21-50, 51-100, 101-150 or >150.
- Sporting activities (type and frequency)
- Ambulatory status, including need for ambulatory assistance devices such as leg braces, cane, crutches, or wheelchair
- Number of bleeding episodes (ABR and annualized joint bleeding rate (ABJR)) categorized by severity within the last 12 months.
- Status of joint health as assessed by physical exam at study enrollment
+ Musculoskeletal evaluation of target joints using HJHS within the last 5 years prior to study enrollment.
- Status of joint health assessed by imaging techniques (e.g. MRI or X-ray)
+radiological evaluation of any joints using the Petterson score within the last 5 years prior to study enrollment.

The following data, if available will be collected at interval and termination visits:

- Total EDs to RIXUBIS since the last visit
- Current RIXUBIS treatment regime (if changed):
 - Dosage and dosing intervals
 - Regimen change date
- Height, Body weight
- FIX inhibitor titer
- Bleed occurrence, including location, etiology, and severity

- Status of joint health as assessed by physical exam
+ Musculoskeletal evaluation of target joints using the HJHS.
- Status of joint health as assessed by imaging techniques (e.g. MRI, X-ray)
+ Radiological evaluation of any joints using the Pettersson score.
- HRQOL measures, surgical data and activity levels (including sporting activities)

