The Hemophilia Joint Health Score (HJHS)¹⁷ was developed by the International Prophylaxis Study Group (IPSG) as a new scoring system for musculoskeletal evaluation optimized for use in children with no or minimal joint disease. The HJHS is better suited for children aged 4–18 years and all patients on primary prophylaxis than the Gilbert score, which was found to be too insensitive to identify earliest signs of joint disease. The HJHS includes the following parameters: swelling, duration of swelling, muscle atrophy, joint pain, crepitus on motion, flexion loss, extension loss, strength and global gait. The HJHS measures joint health, in the domain of body structure and function (i.e. impairment), of the joints most commonly affected by bleeding in hemophilia: the knees, ankles, and elbows. It can be used when there is a need for orthopedic intervention, or as an outcome measure of physiotherapy interventions. It is appropriate for monitoring joint change over time or assessing effectiveness of treatment regimens in children receiving both prophylactic and on-demand therapy. The HJHS 2.1 provides a total score (higher score is worse; max=124), joint specific scores, and a global gait score. See [Table 5](#). The HJHS total score, calculated from the Sum of Joint Totals and Global Gait Score will be collected during screening, annual, and termination visits or whenever the treating physician deems it appropriate.

Table 5 Hemophilia Joint Health Score (HJHS) for assessing Joint Impairment	
Swelling	0 = no swelling 1 = mild 2 = moderate 3 = severe
Duration (swelling)	0 = no swelling or < 6 months 1 = ≥6 months
Muscle Atrophy	0 = none 1 = mild 2 = severe
Joint Pain	0 = no pain through active range of motion 1 = no pain through active range, only pain on gentle overpressure or palpation 2 = pain through active range
Crepitus on Motion	0 = none 1 = mild 2 = severe
Flexion Loss	0 = < 5° 1 = 5° - 10° 2 = 11° - 20° 3 = > 20°
Extension Loss (from hyperextension)	0 = < 5° 1 = 5° - 10° 2 = 11° - 20° 3 = > 20°

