Strength (using the Daniels & Worthingham's scale)	Within available ROM 0 = holds test position against gravity with maximum resistance (gr.5) 1 = holds test position against gravity with moderate resistance (but breaks with maximal resistance) (gr.4) 2 = holds test position with minimal resistance (gr.3+), or holds test position against gravity (gr. 3) 3 = able to partially complete ROM against gravity (gr.3-/2+), or through partial ROM gravity eliminated (gr.2-) 4 = Trace (gr.1) or no muscle contraction (gr.0) NE = non-evaluable
Global Gait (walking, stairs, running, hopping on 1 leg)	0 = all skills are within normal limits 1 = one skill is not within normal limits 2 = two skills are not within normal limits 3 = three skills are not within normal limits 4 = four skills are not within normal limits NE = non-evaluable

Source: Feldman et al, 2008, HJHS Summary Score Sheet at (last accessed August 2014)
http://www1.wfh.org/docs/en/Publications/Assessment_Tools/HJHS_Summary_Score.pdf

- Radiographs using the Pettersson scale (if available)
- The World Federation of Hemophilia endorsed a radiographic scale, commonly referred to as the Pettersson scale ¹⁸ to measure hemophilia joint health status. Eight parameters are weighted and summed to give a score for the joint as shown in [Table 6](#). Pettersson scores of all joints will be collected during screening, intervals, and termination visits or whenever the treating physician deems it appropriate.

Table 6 Pettersson Scale for Radiographic Evaluation of Hemophilic Joints	
X-Ray	
Osteoporosis: Absent: 0 Present: 1
 
Enlarged epiphysis: Absent: 0 Present: 1
 
Irregular subchondral surface: Absent: 0 Surface partially involved: 1 Surface totally involved: 2
 
Narrowing of joint space: Absent: 0 Present with joint space <1 mm: 1 Present with joint space >1 mm: 2
 
Subchondral cyst formation: Absent: 0 1 cyst: 1 >1 cyst: 2
 
Erosion at joint margins: Absent: 0 Present: 1
 
Gross incongruence of articulating bone ends: Absent: 0 Slight: 1 Pronounced: 2
 
Joint deformity (angulation and/or displacement between articulating bones): Absent: 0 Slight: 1 Pronounced: 2

Source: Pettersson H et al 1980 ¹⁸

- Magnetic Resonance Imaging scoring system (if available and used at site)

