- Several MRI scoring systems have been developed to measure hemophilia joint health status. One of the most commonly used systems was one that was developed in Lund, Sweden²³. MRI scores of all joints will be collected during screening, intervals, and termination visits or whenever the treating physician deems it appropriate. The scoring system^{24;25;26} used shall be determined by the subject's radiologist.

Table 7 Magnetic Resonance Imaging Scoring System Developed in Lund, Sweden	
A Component	Subchondral Cyst Present in at least 1 bone Present in at least 2 bones >3 cysts in at least 1 bone >3 cysts in at least 2 bones Largest size >4 mm in at least 1 bone Largest size >4 mm in at least 2 bones Irregularity/erosion of subchondral cortex Present in at least 1 bone Present in at least 2 bones Involve more than half of joint surface in at least 1 bone Involve more than half of joint surface in at least 2 bones Chondral destruction Present in at least 1 bone Present in at least 2 bones Full thickness defect in at least 1 bone Full thickness defect in at least 2 bones Full thickness defect involve s >1/3 of joint surface in at least 1 bone Full thickness defect involves >1/3 of joint surface in at least 2 bones
Effusion/hemarthrosis (e)	Full thickness defect involves >1/3 of joint surface in at least 2 bones
Hypertrophic synovial (s)	0 absent
Hemosiderin (h)	1 equivocal 2 small 3 moderate 4 large

Source: Lundin B et al. 2004²³

INVESTIGATOR ACKNOWLEDGEMENT

PARIXS

STUDY TITLE: Post Authorization RIXUBIS Study

PROTOCOL IDENTIFIER: 251401

ORIGINAL 20 MAR 2015

OTHER PROTOCOL ID(s)

NCT Number: TBD

EudraCT Number: TBD

By signing below, the investigator acknowledges that he/she has read and understands this protocol, understands and abides by the requirements for maintenance of source documentation, and provides assurance that this study will be conducted according to all requirements as defined in this protocol, Non-interventional Trial Agreement, good pharmacovigilance practices, and all applicable regulatory requirements. If applicable, he/she will comply with the requirements for obtaining informed consent from all study subjects prior to initiating any protocol-specific procedures and for obtaining written initial and ongoing ethics committee(s) protocol review and approval.

Signature of Principal Investigator

Date

Print Name of Principal Investigator

Signature of MAH Representative

Date

[name]

Vice President, Clinical Development

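### The HJHS analysis names a bleeding parameter that the score does not contain, and Table 6 scores joint-space narrowing against severity

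*Protocol*

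**What the plan says.** Joint health is a secondary objective (Section 8.3), and Section 9.3.2.3 lists the HJHS, Pettersson and MRI scores among its endpoints, where available.

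**HJHS.** The analysis text in Section 9.7.3.4.3 reads: "Physical exam using only the pain, bleeding, and physical exam parameters of the Hemophilia Joint Health Score (HJHS) score will be summarized", at baseline and at months 12, 24, 36 and 48. Appendix 2 describes the instrument differently: "The HJHS includes the following parameters: swelling, duration of swelling, muscle atrophy, joint pain, crepitus on motion, flexion loss, extension loss, strength and global gait". It gives the range: "The HJHS 2.1 provides a total score (higher score is worse; max=124), joint specific scores, and a global gait score". It also states what sites record: "The HJHS total score, calculated from the Sum of Joint Totals and Global Gait Score will be collected during screening, annual, and termination visits". The joints scored are "the joints most commonly affected by bleeding in hemophilia: the knees, ankles, and elbows". Section 9.2.6, which lists the data for screening and for later visits, asks for this instead: "Musculoskeletal evaluation of target joints using the HJHS".

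**Pettersson.** Table 6 in Appendix 2 scores a joint space that is not narrowed as 0, and then: "Present with joint space <1 mm: 1 Present with joint space >1 mm: 2". Section 9.7.3.4.3 summarises the Pettersson score at the same five timepoints, with interpolation and limited extrapolation.

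**MRI.** Section 9.1.2.3 names the scoring system developed in Lund. Appendix 2 says that the scoring system "used shall be determined by the subject's radiologist".

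**The concern.** The HJHS sentence in the analysis section limits the score to three named parts. One of them, bleeding, is not in the instrument as the protocol defines it. The word *only* signals a subscore, while Appendix 2 has sites collect the total. Whoever programs the analysis has to decide which of the two sections to follow. Section 9.2.6 adds a second disagreement, because a score taken on target joints is not the total over knees, ankles and elbows plus gait. Under Section 9.3.2.3 a joint can gain or lose target status, so the joints scored under a target-joint reading could also change from visit to visit.

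The Table 6 problem is of another kind. If a reader scores from that table, further loss of joint space lowers the score, which then looks like radiographic improvement. Where only the total per joint was recorded, the error could not be undone afterwards.

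**Working it through.** **HJHS: does the item list leave room for a bleeding component?**

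Item maxima from Table 5:

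| Item | Maximum |
|---|---|
| Swelling | 3 |
| Duration of swelling | 1 |
| Muscle atrophy | 2 |
| Joint pain | 2 |
| Crepitus | 2 |
| Flexion loss | 3 |
| Extension loss | 3 |
| Strength | 4 |
| **Per joint** | **20** |
| Global gait (once per subject) | 4 |

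Knees, ankles and elbows on both sides make 6 joints. Total = 6 × 20 + 4 = **124**, which reproduces the maximum stated in Appendix 2. The listed items use up the whole range, so no bleeding item has been left out of the list.

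The three parts named in Section 9.7.3.4.3 compare with Table 5 as follows:

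- *Pain* is an item.
- *Bleeding* is not an item.
- *Physical exam* is not an item name, but the remaining items are all examination findings. On that reading the analysed score covers all joint items (6 × 20 = 120), or 124 if gait counts as part of the examination. The sentence does not say which.

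**Pettersson: is the joint-space item ordered by severity?**

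Item maxima from Table 6: osteoporosis 1, enlarged epiphysis 1, subchondral surface 2, joint space 2, cysts 2, erosion 1, incongruence 2, deformity 2. Sum = 1 + 1 + 2 + 2 + 2 + 1 + 2 + 2 = **13** per joint. The seven items other than joint space all score 0 for absent and rise with presence or extent. A remaining space below 1 mm is more narrowed than one above 1 mm.

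| Change in one joint | As in Table 6 | Ordered by severity |
|---|---|---|
| Not narrowed to >1 mm | 2 − 0 = +2 | 1 − 0 = +1 |
| >1 mm to <1 mm | 1 − 2 = **−1** | 2 − 1 = **+1** |
| Not narrowed to <1 mm | 1 − 0 = +1 | 2 − 0 = +2 |

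For the step from >1 mm to <1 mm the error is +1 − (−1) = 2 points. A joint with the worst finding on every item scores 13 − 2 + 1 = 12 under Table 6, and 13 when the item is ordered by severity.

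**The case against.** Several stronger readings are tempting, and the protocol does not support them.

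- **The HJHS analysis reduces to joint pain, 12 of 124 points, or cannot be computed.** This holds only if *physical exam* must be an item name. Section 9.1.2.3 places the HJHS within the physical examination, and the other items are examination findings, so the natural reading covers nearly the whole score. What remains is a stray component, an *only* that contradicts Appendix 2, and doubt about gait.
- **The total cannot be formed because only target joints are scored.** Section 9.2.6 does not say *only*, and Appendix 2 says outright that the total is collected. The two places are inconsistent, but that does not show that the data will be missing.
- **MRI means will mix scales.** Section 9.7.3.4.3 does not say that scores from different systems will be pooled, and a statistical analysis plan that is not shown may separate them. What stands is that one section names a system while another leaves the choice open.
- **The case report form carries the Table 6 error.** The form is not among the documents. Readers may also score from the published scale that the protocol cites and not from this table.
- **Exactly 1 mm has no score.** Table 6 assigns none. But the cited scale is not available here, and giving that value a score would alter a published instrument on no evidence.

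A fair caution also applies to Table 6. The point rests on two inequality signs in text extracted from PDF by a program. Both signs would have to be reversed for the item to be correct, while other thresholds in Tables 5 and 6 read coherently. That makes an extraction fault unlikely, but the original page should be checked. The primary analysis of bleeding rates does not use any of these scores.

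**Conclusion.** Two defects hold as written. First, Section 9.7.3.4.3 defines the HJHS analysis by a component that the instrument lacks and contradicts Appendix 2 on what is scored; Section 9.2.6 is also out of line with the total. Second, Table 6 orders the joint-space points against severity, which gives a 2-point error on a 13-point scale for a joint moving from >1 mm to <1 mm and caps the worst joint at 12.

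Severity is moderate. The endpoints are descriptive, secondary and recorded only where available; no sample size, test or primary result depends on them.

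The conclusion assumes that the Table 6 signs stand in the original as they do in the extracted text. It also assumes that a higher Pettersson score means worse damage, which the protocol does not state but which all seven other items imply. The 2-point figure takes the other items as unchanged. The MRI point is minor.

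**What to change.** 1. In Section 9.7.3.4.3, replace the restriction to pain, bleeding and physical exam with the HJHS total score as defined in Appendix 2 (joint totals plus global gait, 0 to 124). Report joint-specific scores where the total is not available.
2. Align the HJHS wording in Section 9.2.6 with Appendix 2, so that both ask for the joints and the gait score that the total needs.
3. Check the joint-space signs in Table 6 against the original page and the cited scale. If they stand as extracted, reorder the points so that the smaller remaining space scores higher, and make sure that any scoring form based on Table 6 agrees.
4. Record which MRI scoring system was used, and summarise scores and changes within one system.

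The cost is some wording, one table correction and one data field. Naming the total may leave fewer subjects with a complete HJHS result, and the joint-specific scores partly offset that.
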